3.1.6. Continued Study Drugs Following DLT

In the Phase 1b portion of the study, patients experiencing a DLT will not receive additional study drugs unless all the following conditions are met:

- The DLT has returned to at least Grade 2 or clinically insignificant from baseline
- The DLT is not expected, in the opinion of the Investigator, Medical Monitor and Sponsor representative, to recur based on an intervention such as prophylactic use of appropriate treatment (e.g., prophylactic anti-emetics), or dose reduction from the prior dose
- Continued administration of study drugs is considered to be in the patient's best interest based on the opinion of the Investigator and the study Sponsor

3.1.7. Maximum Tolerated Dose

While this study is not designed to define a MTD for this combination of study drugs, in the event that a DLT is observed, the MTD of VRx-3996 with valganciclovir will be defined as the highest dose administered during Cycle 1 of Phase 1b at which no more than 33% (i.e., ≤ 1 of 6 or 7 patients) experiences a DLT.

3.1.8. Dose Increases for Individual Patients

In an effort to afford patients the greatest likelihood of benefit from study participation, if judged to be in the best interest of the patient by the Investigator, Medical Monitor, and Sponsor representative, patients may receive an escalated dose of VRx-3996 in subsequent cycles. This escalated dose will generally follow the dose levels previously explored in the study and may not exceed the highest dose shown to be safe (i.e., the highest dose that has been demonstrated not to exceed the MTD based on evaluation of at least 3 patients at that level). In addition, no patient

may undergo a dose escalation until having completed at least 2 cycles at their initial assigned dose.

3.1.9. Replacement of Patients during Phase 1b Portion of Study

Patients who are unable to complete the DLT assessment period for reasons other than study drug related toxicity may be replaced if needed to achieve at least 3 patients evaluable for DLTs. The final decision on replacement will rest with the SRC.

In the event that a cohort is filled with 4 patients, and if 1 of the 4 patients is considered not evaluable for safety or for reasons other than study drug related toxicity, this 4th patient will not be replaced, and a decision will be made by the SRC on the safety of the current cohort based on the remaining 3 patients.

3.2. Phase 2 (Dose Expansion)

3.2.1. Phase 2 Sample Size

The Phase 2 portion of the study will accrue 30 patients. Any patients in screening at the time that the 30th patient is enrolled will be permitted to enroll, should they be eligible. This sample size is based on a Simon's 2-stage design where the Phase 2 portion of the study may be stopped if none of the first 10 treated patients have a response. The hypothesized response rate of a poor drug is 5%, while the hypothesized response rate of a good drug would be at least 20%. Using a 1-sided alpha of 0.05 and power of 80%, if at least 1 of the first 10 patients has a response, the Simon's design recommends accruing up to at least 29 total subjects to test the null hypothesis. The probability of stopping early is 59.9% with a type I error rate of 0.0468 (<http://cancer.unc.edu/biostatistics/program/ivanova/SimonsTwoStageDesign.aspx>).

3.2.2. Phase 2 Dose

The dose and schedule of VRx-3996 and valganciclovir used during the Phase 2 portion of the study will be the RP2D for VRx-3996 and valganciclovir as determined by the SRC at the conclusion of the Phase 1b portion of the study.

Based on accumulating efficacy and safety data, the SRC may elect to declare a RP2D prior to defining an MTD or prior to exploring all cohorts listed in [Table 5](#).

The RP2D may be modified later during the Phase 2 portion of the study by the SRC (see [Section 3.2.3](#) and [Section 3.10](#)) if information arises suggesting that the initial RP2D was not appropriate. In the event that the RP2D is adjusted mid-study, all subsequent patients entering the study will receive study drugs at the adjusted RP2D. Patients currently on study at the time of a dose modification may continue with their current dose at the discretion of the Investigator.

3.2.3. Assessment of Toxicity During Phase 2 Dose Expansion

[figure not shown]
Sequential boundaries will be used to monitor the DLT rate during the dose expansion phase of the study.²⁹ If an excessive number of DLTs are seen, the SRC will have the option of either halting study accrual or reducing the RP2D to reduce the level of toxicity. The boundaries at which the study is halted or the RP2D is reduced are listed in [Table 6](#). This is a Pocock-type

boundary that yields at most a 5% probability of crossing the boundary when the rate of DLT is equal to the acceptable rate of 30%.

Table 6: Early Stopping Boundaries for Toxicity

# Patients	1	2	3	4	5	6	7	8	9	10	11	12	13	14	15
Boundary	-	-	-	4	5	5	6	6	7	7	8	8	9	9	9
# Patients	16	17	18	19	20	21	22	23	24	25	26	27	28	29	30
Boundary	10	10	11	11	12	12	12	13	13	14	14	14	15	15	15

3.2.4. Phase 2 Study Drug(s) Administration Schedule

In the Phase 2 portion of the study VRx-3996 will be administered 20 mg PO QD for 4 days on and 3 days off in a 7-day regimen. Valganciclovir will be administered 900 mg PO QD. VRx-3996 and valganciclovir will be taken at the same time for all visits.

The administration schedule used for VRx-3996 and/or valganciclovir may be modified as appropriate by the SRC during the course of the study. Changes to the schedule will be enacted with minimal or no change in the total daily dose.

If employed during the study, the following schedule definitions will be used:

- QD – Once each day at approximately the same time
- Q12 hours – Twice each day at between a 10 to 14-hour interval
- BID – Twice each day at between 8- and 12-hour intervals (preferably at 12-hour intervals when possible)

The SRC may define and employ other schedules as appropriate based on data accumulated during the course of the study.

3.3. Tablet Cohort

Once the Phase 2 arm has completed enrollment, approximately 10 patients will be enrolled into a cohort to receive VRx-3996 tablets instead of capsules. Approximately 10 patients will be needed to provide an assessment of systemic exposures to VRx-3996. The dose and schedule of VRx-3996 and valganciclovir administered to patients in the tablet cohort will be the RP2D

(VRx-3996 20 mg PO QD for 4 days on and 3 days off in a 7-day regimen with valganciclovir 900 mg PO QD starting at C1D1). VRx-3996 and valganciclovir will be taken at the same time for all visits.

The intent of these evaluations will be important to the clinical development program for assessing comparability of exposures to VRx-3996 administered as a tablet presentation, for comparison to delivery of the oral capsule product. The tablet form of VRx-3996 allows for a reduction from four 5 mg capsules to two 10 mg VRx-3996 tablets per dose on a daily basis and is expected to be less of a burden for patients.

With exceptions as described in the protocol, patients will follow the protocol/assessments as detailed for the Phase 2 expansion cohort patients.

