3.1. Phase 1b (Dose Escalation)

3.1.1. Cohort Size

Cohort size during the Phase 1b portion of the study will be up to 7 patients using a conventional modified 3+3 design for dose escalation studies in oncology. The first cycle (28 days) is defined as the DLT assessment period. At each dose level, 3 or 4 patients will initially be enrolled and followed through the DLT assessment period. If 1 patient in the initial 3 or 4 patients experiences a DLT, the cohort will be expanded to 6 or 7 total patients.

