2.2 Secondary Study Objectives

The secondary objectives of this study include the following:

- Evaluate pharmacokinetic (PK) profile of varying doses of nanatinostat in capsule form and in tablet form (at RP2D only for tablet form)
- Evaluate PK parameters of varying doses of valganciclovir
- Evaluate time to response (TTR)
- Evaluate duration of response (DoR)
- Determine progression-free survival (PFS) and overall survival (OS)

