Plasma PK parameters will be presented in data listings and summarized separately using descriptive statistics (number of subjects (N), number of observations (n), arithmetic mean, SD, CV%, geometric mean, geometric CV%, median, minimum, and maximum) by treatment. T_{max} will be summarized using number of observations, median, minimum, and maximum only.

Plasma PK parameters will be displayed to 3 significant figures in all data listings and summary tables except for CV%, which will be reported to 1 decimal place. Time variables (t_{max} , λ_z lower, and λ_z upper) will be displayed to 2 decimal places.

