4.7.4 Pharmacokinetic Inferential Statistics

The dose proportionality of the key nanatinostat PK parameters C_{max} , $AUC_{0-\infty}$ and AUC_{0-6h} , if appropriate over the administered dose range, will be assessed using the following model using all dose groups:

$$\log(\text{parameter}) = a + b * \log(\text{dose})$$

where 'a' is the intercept and 'b' is the slope. The model will be fit to the pooled, individual group patient data. Parameter estimates of b, including the standard error and 90% CIs will be summarized in a table. If the 90% CI for b includes 1.0, then linearity will be concluded.

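### The tablet cohort is meant to assess exposure comparability with capsules, but the SAP plans only separate descriptive summaries, with no tablet/capsule ratio or confidence interval

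*Protocol*

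**What the plan says.** Protocol 3.3 describes the tablet evaluations as important for "assessing comparability of exposures to VRx-3996 administered as a tablet presentation, for comparison to delivery of the oral capsule product". On size it says "Approximately 10 patients will be needed to provide an assessment of systemic exposures to VRx-3996", without a variability figure, target precision or margin. The secondary PK objective (Protocol 2.2, SAP 2.2) is to evaluate PK in each form, the tablet at the RP2D only.

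SAP 4.7.3 says "Plasma PK parameters will be presented in data listings and summarized separately using descriptive statistics". The listed statistics include n, geometric mean and geometric CV%, by treatment. SAP 4.7.2 overlays the mean concentration curves of all treatments. SAP 4.1.1 presents tables by cohort and study phase, with an extra column for everyone who received capsules.

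SAP 4.7.4, the only inferential PK section, addresses "The dose proportionality of the key nanatinostat PK parameters". It regresses log(parameter) on log(dose) over all dose groups, with the rule "If the 90% CI for b includes 1.0, then linearity will be concluded". There is no formulation term. SAP 4.1 states that cohorts will not be formally compared, and SAP 4.6.5.7 disclaims equivalence between drug products. SAP 4.9, which lists departures from the protocol, does not mention the tablet/capsule comparison.

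**The concern.** The protocol names a comparative question and the SAP stops one step short of it. Two adjacent columns with large CVs invite the remark that exposures look similar, because neither column shows the uncertainty of the contrast between them.

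The question has some weight. Protocol 5.1.2 says tablets are intended to replace capsules and that no dose adjustment is needed, and the support it cites is in vitro dissolution and dog PK. The tablet cohort is the only source of human tablet exposure data that the documents describe.

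The comparator is also left open. The all-capsule column mixes the Phase 1b doses (5, 10 and 20 mg per administration) with Phase 2. Protocol 12.4.1 names the Phase 1b cohorts and the tablet cohort for PK summaries but not the Phase 2 capsule patients. Under SAP 4.7.2, Cycle 2 Day 1 serial profiles exist for only some Phase 2 capsule patients.

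**Working it through.** **Plan's own figure.** There is none to reproduce: the size of about 10 comes with no CV, confidence level, margin or interval width. What can be checked is the precision that such a comparison would have.

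**Inputs.**
- Tablet patients: 10 (Protocol 3.3).
- Capsule patients at the RP2D: 30 (Protocol 3.2.1: "The Phase 2 portion of the study will accrue 30 patients").
- Cohort 3, capsules at the same dose and schedule: at most 7 (Protocol 3.1.1: "Cohort size during the Phase 1b portion of the study will be up to 7 patients").
- Between-patient CV: Protocol Table 4. Cmax CVs run from 68% to 167% and AUC0-∞ CVs from 57% to 138%. At 20 mg the Cmax CV is 68% from 3 patients, and AUC0-∞ has one reliable observation, so no CV. At 40 mg the AUC0-∞ CV is 74% and the Cmax CV 100%. Applying these figures to this trial is an assumption.
- Confidence level: 90%, as SAP 4.7.4 already uses for the dose slope.

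**Formula.** Two independent groups on the log scale:

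s = √ln(1 + CV²)

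h = t(0.95; n₁ + n₂ − 2) × s × √(1/n₁ + 1/n₂)

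90% CI = observed ratio × exp(±h)

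**10 tablet against 30 capsule.** t(0.95; 38) = 1.686 and √(1/10 + 1/30) = 0.365. For CV 68%: s = √ln(1.4624) = 0.617, h = 1.686 × 0.617 × 0.365 = 0.380, and exp(±0.380) = 0.68 and 1.46.

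| CV | s | h | 90% CI if observed ratio is 1.00 |
|---|---|---|---|
| 57% | 0.530 | 0.327 | 0.72–1.39 |
| 68% | 0.617 | 0.380 | 0.68–1.46 |
| 74% | 0.661 | 0.407 | 0.67–1.50 |
| 100% | 0.833 | 0.513 | 0.60–1.67 |
| 138% | 1.033 | 0.636 | 0.53–1.89 |
| 167% | 1.154 | 0.711 | 0.49–2.04 |

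**Does the comparator matter?** Adding 7 Cohort 3 patients (37 capsule) barely changes the result: 0.67–1.49 at CV 74%, because the 10 tablet patients dominate the variance. Using Cohort 3 alone as comparator widens it: 0.59–1.70 at CV 68% and 0.57–1.77 at CV 74%.

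**Can SAP 4.7.4 supply the answer indirectly?** No. Tablet patients all receive 20 mg, so a model in dose alone cannot separate formulation. If they are included among all dose groups, a formulation difference would feed into the dose slope.

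**The case against.** The best defence is that the descriptive approach is declared and coherent. Protocol 12.4.1 promises descriptive PK summaries for the tablet cohort, the secondary objective is to evaluate each form, SAP 4.1 plans no formal cohort comparison, and SAP 4.6.5.7 disclaims equivalence. No decision rule in the documents hangs on a tablet/capsule ratio. All of this stands: the plan contains no wrong figure here. It does not remove the gap, because a ratio with an interval is estimation, not a test, and the SAP already reports a 90% CI in its PK section.

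Some stronger readings are tempting but unsupported.

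- A reader might infer that the SAP offers no comparison at all and hides the imprecision. It does not: summaries by cohort and phase, geometric means, geometric CV%, n and overlaid curves allow a side-by-side reading, and a careful reader could compute a ratio and interval by hand. What is missing is the planned contrast and a named comparator.
- A reader might infer that the patients are enrolled solely for this question. Protocol 12.2 includes the tablet cohort in the study's outcome analysis, and Protocol 3.3 has them follow the Phase 2 assessments.
- A reader might call the cohort too small for bioequivalence. The documents set no equivalence margin and disclaim that aim, so this is no fault against the plan.
- A reader might take the Table 4 CVs as this trial's variability. They come from a single-agent study in solid tumours, and the figure at 20 mg rests on 3 patients.

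**Conclusion.** The point holds as a mismatch between Protocol 3.3 and the SAP: the stated purpose is comparative, while the planned analysis is a set of separate summaries with no tablet/capsule ratio or interval.

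Over the Table 4 CV range of 57% to 167%, an observed ratio of 1.00 with 10 against 30 patients would be compatible with true ratios from 0.72–1.39 at best to 0.49–2.04 at worst, and 0.68–1.46 at the 20 mg Cmax CV. Even at the lowest CV, differences of about 30% in either direction are not excluded.

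This rests on log-normal exposures, a common variance, independent groups, full PK evaluability and the transfer of earlier-study CVs. AUC0-∞ may have fewer usable patients, because SAP 4.7.3 drops values with more than 20% extrapolation. The cohorts are sequential and non-randomised, and the interval does not reflect any confounding from that.

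**What to change.** Add one analysis to SAP 4.7.4: the tablet/capsule geometric mean ratio with 90% CI for Cycle 1 Day 1 nanatinostat, from a log-scale model with formulation as factor.

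- **Parameters:** Cmax and AUC0-6h (both already key parameters in SAP 4.7.4) and, where estimable, AUC0-8h and AUC0-∞. State n for each.
- **Comparator:** Phase 2 capsule patients at the RP2D, not the pooled all-capsule column. Add Cohort 3 only as a sensitivity analysis, because the Cycle 1 Day 1 dosing sequence changed with Protocol Amendment 4.0 (Protocol 3.1.3) and Cohort 3 patients may have been dosed differently on that day.
- **Label:** estimation only, not equivalence, in line with SAP 4.6.5.7, with a note that the cohorts are sequential and non-randomised.

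Cycle 1 Day 1 serial samples are planned for all patients (SAP 4.7.2), so no new sampling is needed. The cost is one SAP paragraph, one table and an interval that will look wide.

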3.4. Continuation of VRx-3996/Valganciclovir

Patients may continue to receive VRx-3996/valganciclovir provided the following criteria are met:

- Patient does not demonstrate progressive disease (in the absence of clinical deterioration, patients may continue on study drug until a repeat scan confirms progression)
- Patient has not experienced unacceptable toxicity that cannot be resolved with supportive treatment, a dose reduction, or interruption
- The Investigator considers additional VRx-3996/valganciclovir to be in the best interest of the patient

3.5. Dose Adjustments/Modifications/Delays

Details on dose adjustments, modifications, and delays are outlined in [Section 5.1.8](#) and [Section 5.2.5](#).

Patients who have had a dose hold should continue to follow all assessments called for in the Schedule of Events (i.e., if a patient undergoes a dose interruption, this will not delay conduct of any study procedures).

3.6. Central Pathology Review

A central review of pathology may be performed on available (archived or fresh) tumor samples taken from patients. This will include any historical diagnostic samples and samples available at the time of study entry in addition to samples taken per standard of care during study participation and samples taken at the time of relapse. Archived samples will be used to further characterize the tumor. Presence of EBV for eligibility will be determined by either a local or central pathology lab. Patients enrolled on the basis of a local result will have repeat testing at a central laboratory. The process for submitting archived tissue and procedures for central pathology review will be covered in a separate Study Manual.

3.7. Laboratory Procedures

Sites may elect to use either central or local laboratory tests for purposes of eligibility, safety, and other study required tests. The central laboratory kits should be utilized for the protocol-specified exploratory tests.

Any local labs collected for eligibility, or required by the study protocol, or to make treatment decisions will be entered into the electronic case report forms (eCRF).

The process for submitting central laboratory samples will be covered in the Laboratory Manual.

3.8. Central Radiology Review

Central review of patient scans (CT, MRI, PET-CT) will be performed by the Sponsor. A de-identified digital copy of each scan accompanied by the local radiology report will be generated by the site and sent to the Sponsor for review. The specific scan format and method of transfer will be arranged with each site. The review performed centrally may include an assessment based on both the Lugano²³ and RECIL²³ criteria.

3.9. Central ECG Review

Central review of patient ECGs will be performed by the Sponsor. A de-identified copy of each scan will sent to the Sponsor for review. The specific format and method of transfer will be arranged with each site. The Sponsor may elect to review all ECGs or a subset.

3.10. Safety Review Committee (SRC)

An SRC will govern the conduct of the study. The SRC will consist of the following individuals appointed by the Sponsor:

- Study Investigators
- The Study Medical Monitor
- A Sponsor representative

Responsibilities of the SRC will include:

- Reviewing study safety data throughout conduct of the study
- Confirming or modifying the specific dose escalations between cohorts
- Defining intermediate dose levels as appropriate
- Declaring the MTD (if reached)
- Determining the RP2D
- Providing guidance on treatment-related issues raised by an Investigator

The SRC will meet at the end of each cohort during the Phase 1b portion and approximately quarterly during the Phase 2 portion, or as needed based on the rate of enrollment.

A Core SRC consisting of 2 investigators and 1 clinical expert appointed by the Sponsor will assess the toxicity during Phase 2 dose expansion ([Section 3.2.3](#)).

3.11. Concomitant Medications, Treatments, and Procedures

Drug-interaction studies with VRx-3996 have not been conducted. During their participation on this study, patients may continue to use concomitant medications, treatments, and procedures previously prescribed to treat non-cancer related conditions provided that, in the Investigator's judgment, they will not interfere with the study outcomes. Concomitant medications will be documented until 28 days following the last dose of study drug, or until a new anti-cancer therapy is started if sooner than 28 days.

3.11.1. Cytochrome P450 Substrates

A study with recombinant human cytochrome P450 isoforms (CYP450) suggests that VRx-3996 is a direct inhibitor of CYP3A4 isoform. *In vitro* studies indicated that VRx-3996 is not metabolized by or induces the activity of CYP3A4. A potential for drug interactions between VRx-3996 and drugs that are substrates of CYP3A4 is low but cannot be ruled out (see [Table 18a](#) in the Appendix). Please refer to the Investigator Brochure for detailed description.

3.11.2. Transporter Substrates and Inhibitors

Transporter studies indicate VRx-3996 is likely a substrate of MDR1 and BCRP transporters, but not an inhibitor of these transporters. Therefore, the protocol should limit or restrict strong MDR1/P-gp and BCRP inhibitors relevant to the patient population when administered with VRx-3996 (see [Table 18b](#) in the Appendix).

The effect of gastric pH on study drug absorption is not known. Unless necessary for patient care, proton pump inhibitors and H2 antagonists should be avoided, and antacids should not be given in the 2 hours prior to or within 4 hours post VRx-3996 administration.

3.12. Prophylactic Medications, Treatments, and Procedures

With the exception of prophylactic medications intended to reduce the risk of Tumor Lysis Syndrome (TLS) in patients at risk for TLS, the use of prophylactic medications intended to reduce toxicity associated with VRx-3996/valganciclovir will not initially be allowed.

The SRC may elect to institute the use of prophylactic medications (e.g., for prevention of nausea and vomiting secondary to study drugs) during the study. The specific medications used will be in keeping with generally accepted standards of care and the institutional guidelines of the participating sites.

Prophylaxis for Tumor Lysis Syndrome (TLS)

Patients considered to be at risk for TLS based on specific characteristics (e.g., specific diagnosis, renal insufficiency, bulky disease, elevated lactate dehydrogenase [LDH]) should receive TLS prophylaxis.²⁴

The determination of a patient's risk for TLS can be estimated based on [Table 7](#).

Table 7: Patient Stratification by Risk (adapted from Coiffier 2008)²⁴

Type of Cancer	High risk	Intermediate risk	Low risk
NHL	Burkitt's, lymphoblastic, B-ALL	DLBCL	Indolent NHL
ALL	WBC \geq 100,000	WBC 50,000–100,000	WBC \leq 50,000
CLL		WBC 10,000–100,000	WBC \leq 10,000

Abbreviations: ALL = acute lymphoblastic leukemia; B-ALL = Burkitt's acute lymphoblastic leukemia; CLL = chronic lymphocytic leukemia; DLBCL = diffuse large B-cell lymphoma; NHL = **non-Hodgkin's lymphoma**.

Patients considered at high risk for TLS should be managed in the inpatient setting with increased laboratory monitoring during the first 48 hours. Patients should receive rasburicase based on the recommended dosing outlined in [Table 8](#).

Table 8: Recommended Rasburicase Dosing (adapted from Coiffier 2008)²⁴

Risk profile	Baseline uric acid		Dose (mg/kg)*	Duration
	mg/dL	mmol/L		
High	>7.5	>450	0.20	Based on plasma uric acid levels
Intermediate	<7.5	<450	0.15	Based on plasma uric acid levels
Low	<7.5	<450	0.10	Clinical judgement

* Sites may choose to follow institutional standards for dosing rasburicase if they differ from those outlined in [Table 8](#).

Patients should also receive hydration with fluid intake maintained at approximately 1 to 2 times maintenance, with a urine output of 80 to 100 mL/m²/hour.²⁴

